USING LATENT VARIABLES AND DIRECTLY OBSERVED TREATMENT TO IMPROVE THE DIAGNOSIS AND MANAGEMENT OF DEPRESSION AMONG HEMODIALYSIS PATIENTS

Date: October 3, 2017

NCT Number: NCT03390933

Statistical analyses

Develop and validate hemodialysis-specific depression screening instrument. We will begin by using graphs and descriptive statistics to summarize demographic and medical characteristics as well as scores on our measures of depression (PHQ-9) and dialysis complications. Next, we will perform exploratory factor analysis of the nine PHQ-9 items to determine how many latent factors represent aspects of depression. It has been hypothesized that the PHQ-9 has a two factor structure representing somatic and affective domains of depression. However, our previous work on depression and multiple sclerosis suggested a single factor structure. We will use an oblique (geomin) rotation and will examine the eigenvalues, which represent the variance accounted for by each underlying factor, in a scree plot. The number of eigenvalues ≥ 1 represent unique latent factors. We will also use parallel analysis to calibrate our decisions regarding meaningful eigenvalues. This approach computes eigenvalues from a random dataset via Monte Carlo simulation with the same number of observations and variables as used in the factor analytics model. Further, we will use model fit criteria such as chi-square, comparative fit index (CFI), Tucker Lewis fit index (TLI), root mean square error of approximation (RMSEA), and standardized root mean square residual (SRMR) statistical test values to help determine the measurement properties of our latent constructs.

We will then use structural equation modeling to examine overlap between depressive symptoms and dialysis complications. Conducting these analyses involves four steps: 1) specifying the conceptual model, 2) estimating model parameters and assessing goodness of fit, 3) making any model modifications, and 4) testing hypotheses of interest. In particular, we will apply a measurement model with covariates which permits detection and adjustment for differential item functioning (DIF), i.e. when subgroups with the same latent trait have a different likelihood of responding to specific questions.⁷⁹ The initial model will include the factors representing aspects of depression, depressive symptoms, dialysis complications, and all the potential paths (referred to as DIF paths) connecting them. We will then make model comparisons and modifications to our initial model using multiple indices and statistics (e.g. chi-square, CFI, TLI, RMSEA, SRMR, modification indices) along with clinical input to establish the best fitting model, i.e. the most parsimonious model with all clinically relevant DIF paths of at least a small standardized path coefficient.⁸⁰ The results of these analyses will be standardized path coefficients which indicate the magnitude of the effect of one variable on another such as the impact of nocturnal cramps on sleep disturbance after adjustment for all other relationships in the model.²⁹ Both factor analysis and structural equation modeling will be performed with MPlus software.⁸⁰

For clinical use, we will develop a hemodialysis-specific PHQ-9 (hdPHQ-9) free of overlapping symptoms to isolate the underlying dimension of depression. We will extract factor scores from the latent construct (or constructs) representing depression in the final best fitting model to form this adjusted scale. A factor score is an individualized score on a latent construct representing a scale of interest. These factor scores will be linearly transformed to fit the range of the original PHQ-9 (i.e. 0–27) using a probability integral transformation to maintain the interpretation and thresholds of the PHQ-9. This one-to-one transformation will result in similar distributions of PHQ-9 and hdPHQ-9 scores in the sample. However, certain individuals will have sizeable differences between the two scores. We will also develop a web app that will allow users to enter information for a patient and will automatically calculate the hdPHQ-9 score.

Finally, we will use bootstrapping in order to validate our hdPHQ-9. After developing our model

based on the entire sample, we will fit the model on a series of bootstrap datasets (each by resampling with replacement the same number of observations as the entire sample). From this

procedure we will: 1) obtain the average (as well as the 95% confidence interval) for each of the model parameters and fit indices across the bootstrap samples and 2) observe how the extracted hdPHQ-9 factor scores for each individual in the original data set vary across the models derived from each bootstrapped sample. Thus, bootstrapping validation can be used to understand if there is any bias and sampling variation in the model parameters and associated hdPHQ-9 scores due to overfitting in the final model.

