## ABSTRACT

Depression is present in about 20-30% of hemodialysis patients and is associated with morbidity and mortality. However, depression is inadequately diagnosed and treated among dialysis patients. This is due in part to the overlap between depressive symptoms (e.g. appetite change, trouble sleeping, feeling tired) and symptoms related to persistent metabolic derangements in hemodialysis patients (e.g. nausea, nocturnal cramps, feeling washed out after treatment). The overlap between depressive symptoms and dialysis-related complications makes it difficult to diagnose and therefore to treat depression. In addition, prescription of antidepressant medication may increase an already high pill burden and result in poor adherence. Moreover, the evidence base to guide depression treatment among hemodialysis patients is limited. In our previous work, we developed methods to use latent variables and structural equation modeling to isolate depressive symptoms. Other investigators have demonstrated that directly observed treatment enhances the effectiveness of tuberculosis and HIV treatment.

We now propose a cross-sectional study (Phase 1) followed by a randomized controlled trial (Phase 2) at 17 dialysis facilities. The cross-sectional study will involve assessments of depressive symptoms (using the PHQ-9 screening instrument) as well as dialysis-related complications (KDQOL) in about 1083 patients. We will then use structural equation modeling to develop and validate a hemodialysis-specific PHQ-9 (hdPHQ-9) that will isolate depressive symptoms. The trial will involve 216 patients with confirmed depression who will be randomly assigned to (a) directly observed weekly antidepressant treatment with fluoxetine or (b) referral to their nephrologists, their primary care physicians, or nearby mental health providers. The primary outcome of the trial will be remission of depression at 12 weeks. The trial results will also be used to compare the responsiveness of the PHQ-9 and the hdPHQ-9. We anticipate that the hdPHQ-9 will be a valid and responsive instrument that will isolate depressive symptoms in hemodialysis patients and ultimately improve the screening and diagnosis of depression. We also expect that directly observed weekly fluoxetine treatment will be an effective way to manage depression among hemodialysis patients.

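### Does the SAP need to name anchor items before the initial model of PHQ-9 overlap with dialysis complications can be fitted?

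*SAP*

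**What the plan says.** The SAP, under Statistical analyses, first uses exploratory factor analysis to decide how many factors the nine PHQ-9 items carry. It mentions the hypothesis that "the PHQ-9 has a two factor structure representing somatic and affective domains of depression", but also that the team's earlier work in multiple sclerosis suggested one factor.

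It will then "apply a measurement model with covariates which permits detection and adjustment for differential item functioning (DIF"), where DIF means different responses to an item among people at the same level of the latent trait. Specifying the conceptual model is the first of four listed steps. The initial model holds the factors, the symptoms, "dialysis complications, and all the potential paths (referred to as DIF paths) connecting them". It is modified "using multiple indices and statistics (e.g. chi-square, CFI, TLI, RMSEA, SRMR, modification indices) along with clinical input" until the analysts reach "the most parsimonious model with all clinically relevant DIF paths of at least a small standardized path coefficient".

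Factor scores from that final model become the hdPHQ-9. They are put on the 0 to 27 scale "using a probability integral transformation to maintain the interpretation and thresholds of the PHQ-9". No list of free and fixed paths and no anchor item is given.

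**The concern.** In this kind of model the data show only how strongly each PHQ-9 item rises with each complication. That slope is the sum of a direct effect on the item (DIF) and an effect passing through depression. Separating the two is the purpose of the hdPHQ-9, and a constraint has to do it. If the constraint is not written down, it could be chosen after the scores have been seen.

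Fit would not always expose a poor choice. A model with all item paths free and no factor paths fits exactly as well as one with a single DIF-free anchor per factor, so chi-square, CFI, TLI, RMSEA and SRMR cannot choose between them. The planned bootstrap refits the chosen model, so it cannot choose either.

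Because the PHQ-9 cut-offs are kept, two constraints could place the same patient on different sides of the threshold. Under the assumptions set out below, between 58 and 166 of 1083 patients would differ between the two versions.

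**Working it through.** **Inputs.** Nine items and one or two factors (SAP). About 1083 Phase 1 patients (Protocol, Abstract). The number of complications is not stated; 10 is assumed, because the Protocol (Data elements, Quality of life) adds 10 complication symptoms to the KDQOL-36. Items are treated as continuous, and with two factors each item loads on one.

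**What is identified.** For item j and complication k:

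slope(j,k) = DIF(j,k) + loading(j) × factor path(k)

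The data supply 9 × 10 = 90 slopes. The residual covariances identify 9 loadings + 9 residual variances = 18 parameters for one factor, and 19 with a factor correlation. The rank therefore cannot exceed 90 + 18 = 108, or 90 + 19 = 109.

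| Initial model | One factor: parameters / rank | Two factors: parameters / rank |
|---|---|---|
| All item and factor paths free | 90 + 10 + 18 = 118 / 108 | 90 + 20 + 19 = 129 / 109 |
| Item paths only | 90 + 18 = 108 / 108 | 90 + 19 = 109 / 109 |
| One anchor per factor, factor paths free | 80 + 10 + 18 = 108 / 108 | 70 + 20 + 19 = 109 / 109 |
| Plausible paths: 3 items per complication, factor paths free | 30 + 10 + 18 = 58 / 58 | 30 + 20 + 19 = 69 / 69 with five somatic items; 69 / 59 if the somatic factor has only those three |

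The first row falls short by one parameter per complication per factor. The second is identified, but with a loading of 0.7 and a true factor path of 0.3 it shows DIF of 0.7 × 0.3 = 0.21 on every item. The last row works unless one factor has no untouched item.

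**Which row the SAP describes.** Three features point to the last row. The conceptual model comes first, and the Protocol timetable schedules its refinement during development. Modification indices are to be used, yet in the first two rows no complication-to-item path is left out for them to flag. DIF is defined at equal latent trait, which fits badly with forcing depression to be unrelated to complications.

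**Does the parsimony rule find the right split?** Take one complication, all loadings 0.7 and a true factor path of 0.3. The true model keeps k DIF paths when k of 9 items are affected.

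- Equal DIF of 0.2: the rival model sets the factor path to 0.3 + 0.2/0.7 = 0.586, clears the k affected items and keeps 9 − k paths. The true model is sparser while k < 9 − k, that is up to k = 4.
- Unequal DIF (0.1 to 0.4): a rival can clear only one affected item, so it keeps 8. The true model is sparser up to k = 7 and ties at k = 8.
- Equal DIF on 5 items, loadings spread from 0.5 to 0.85: 5 paths against 8.
- A three-item factor with two items affected: the rival wins 1 to 2 under equal DIF, and there is a tie at 2 under unequal DIF. With all three affected the true model loses (3 against 0 or 2).

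The Protocol's own examples are three items: "overlap between depressive symptoms (e.g. appetite change, trouble sleeping, feeling tired) and symptoms related to persistent metabolic derangements in hemodialysis patients". With one factor and 3 of 9 affected, the count is 3 against 6 or 8, and the rule picks the true model.

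**Reclassification.** This compares the item-paths-only score with the anchored score, with no true DIF and before any pruning. Let R² be the share of depression variance explained by complications (assumed). With nine loadings of 0.7, information = 9 × 0.49/0.51 = 8.65; reliability = 8.65(1 − R²)/[1 + 8.65(1 − R²)]; v = (1 − R²) × reliability; correlation = √[v/(R² + v)].

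| R² | Reliability | v | Correlation | Patients of 1083 changing side (20% to 30% above the cut-off) |
|---|---|---|---|---|
| 5% | 0.891 | 0.847 | 0.97 | 58 to 72 |
| 9% | 0.887 | 0.807 | 0.95 | 78 to 97 |
| 25% | 0.866 | 0.650 | 0.85 | 133 to 166 |

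**Is a one-anchor baseline better?** Simulation: n = 1083, 10 complications correlated 0.3, loading 0.7, three true DIF paths of 0.25, cut-off 0.10, 400 replicates; all but n assumed. The figures are shares of null paths wrongly reaching the cut-off.

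| Factor path per complication | Item paths only | One clean anchor | One anchor with DIF of 0.25 on one complication |
|---|---|---|---|
| 0.05 | 2.5% | 0.5% | about 10% |
| 0.10 | 15% | 0.5% | about 10% |
| 0.15 | 52% | 1.0% | 10% |

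With a factor path of zero, item paths only gives 0.3% to 0.4% and the contaminated anchor again about 10%.

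**The case for a change.** The strongest case for a change is that the omission is real, the literal model cannot be estimated, and writing the paths down needs no new data. A simple parameter count would not reveal the defect: with all paths free it leaves 135 − 118 = 17 degrees of freedom for one factor and 135 − 129 = 6 for two. Failure is also possible under the natural reading, if the factor analysis returns a somatic factor made up only of the overlapping items.

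The identification result stands, and so does that last case. The consequence is weaker than it looks. An unidentified start would probably be flagged by the software, and it has to be repaired before any score exists. The 58 to 166 patients come from an unpruned model, whereas the SAP scores only the final one. They measure disagreement between two versions, not error. They also take 20% to 30% as the share scoring 10 or more, while the Protocol says "Depression is present in about 20-30% of hemodialysis patients", which is a prevalence.

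Nor is the suggested remedy a clear gain. One anchor per factor fits identically to the model it would replace. It does worse when the anchor is contaminated and factor effects are near zero, and better when they are 0.10 or more. A start with no DIF paths, extended by modification indices, is also identified. The choice among these belongs to the analysts and their clinical colleagues.

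**Conclusion.** No change to the plan follows. The SAP leaves its identifying constraints unstated, and a literal all-paths start falls short by 10 parameters (one factor) or 20 (two factors) with an assumed 10 complications. The analysts must close this gap to fit anything. The conceptual-model step, the parsimony rule and clinical input make a sensible closure likely. Under the natural reading the model is identified whenever each factor keeps an untouched item for every complication. With exact zeros and unequal DIF, the sparsest model is the true one with up to 7 of 9 items affected; under equal DIF and equal loadings, with up to 4.

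The conclusion assumes overlap limited to a few items, as the Protocol's examples suggest. It is weakest for a somatic factor with only three items. A path diagram may also exist outside the text available, since the Protocol refers to a diagram that is not shown. The reach is limited to developing the hdPHQ-9 and its later responsiveness comparison. The Protocol (Study design overview and timetable) keeps the new score out of screening and response decisions until it has been assessed, and the trial's primary outcome does not use it.

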**Patient characteristics.** Captured by “Chart Abstraction Eligibility.” Included on these forms are demographic variables to be obtained by chart abstraction include age, gender, race/ethnicity. Medical variables will be cause of renal failure, number of years on dialysis, and possible depressive treatment and/or medications. Also, a “Screening interview” will be done to ensure cognitive ability and confirm no current depression treatment.

**Patient Health Questionnaire (PHQ-9).** The PHQ-9 is a 9-item questionnaire that asks about depressive symptoms (listed in section 3.01). In the general population, the PHQ-9 has good internal reliability (Cronbach’s  $\alpha$  of 0.89) and validity (sensitivity and specificity both 88% for major depression diagnosed by structured diagnostic interview). A small study of dialysis patients found similarly high sensitivity and specificity (both 92%). **However, it is not surprising that PHQ-9 scores correlate strongly with structured interview diagnoses of depression because both address the same 9 symptoms.** The main difference between them is that the structured interview tries to determine if symptoms may be due to another

psychiatric condition such as bipolar disorder. We selected the PHQ-9 (rather than other depression screening instruments) because it is brief, is commonly used, and will allow us to build on our previous work on symptom overlap in multiple sclerosis.

**Quality of life.** We will also use the KDQOL assess quality of life. This widely used instrument includes both general scales on health-related quality of life as well as scales that target specific areas relevant to end stage renal disease. 10 additional dialysis complication symptoms have been added to the KDQOL-36

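### The hdPHQ-9 differs from the PHQ-9 in item weighting as well as in overlap adjustment, so differences between the two scores need a no-DIF factor score before they can be credited to overlap removal

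*SAP*

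**What the plan says.** The SAP (Statistical analyses) sets the purpose: "we will develop a hemodialysis-specific PHQ-9 (hdPHQ-9) free of overlapping symptoms to isolate the underlying dimension of depression". The method follows: "We will extract factor scores from the latent construct (or constructs) representing depression in the final best fitting model to form this adjusted scale". That final model contains the paths from dialysis complications to PHQ-9 items, which the SAP calls DIF paths. The factor scores are rescaled to 0–27 "using a probability integral transformation to maintain the interpretation and thresholds of the PHQ-9", and the map is described as one-to-one. The SAP then says of the PHQ-9 and hdPHQ-9: "However, certain individuals will have sizeable differences between the two scores". It gives no cause for those differences.

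The comparator is the ordinary PHQ-9. Protocol, Data elements: "The PHQ-9 is a 9-item questionnaire that asks about depressive symptoms". Nine items on a 0–27 range means 27/9 = 3 points per item at most, so it is an equal-weight sum. Protocol, Abstract: "The trial results will also be used to compare the responsiveness of the PHQ-9 and the hdPHQ-9". No intermediate score is named.

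The other SAP analyses do different jobs. The exploratory factor analysis sets the number of factors. The standardized path coefficients measure overlap item by item. The bootstrap checks the stability of the adjusted model's parameters, fit indices and scores.

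**The concern.** Moving from the PHQ-9 to the hdPHQ-9 changes two things together:

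1. Item responses are adjusted for dialysis complications. This is the scientific question.
2. The equal-weight sum becomes a factor score, in which items with higher loadings count for more.

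No planned score changes only one of these. The rescaling preserves order, so it cannot undo the second change. With unequal loadings, patients would be re-ranked, and some would cross 10, even if complications had no effect on any item.

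What is at stake is interpretation. The new score is offered as "free of overlapping symptoms to isolate the underlying dimension of depression". If patients move across a threshold, or the hdPHQ-9 proves more responsive, a reader will credit removal of overlap. Part of the difference, possibly most of it, could come from item weighting.

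**Working it through.** The plan states no figure on this point, so there is none to reproduce. The size was checked by simulation.

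**From the documents.** Sample size: "dialysis-related complications (KDQOL) in about 1083 patients". Nine items, 0–27 range, cut-off 10 (Protocol, Screening & Study sample), order-preserving rescaling (SAP).

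**Assumed, because the documents do not give them.** One factor. Loadings equal (0.70), mildly unequal (0.60–0.80) or widely unequal (0.45–0.85). Item thresholds giving 22–25% at PHQ-9 ≥ 10. Overlap on sleep, fatigue and appetite, with path β = 0, 0.20 or 0.35. Correlation of complications with depression 0.3.

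**Model.** y*ⱼ = λⱼη + βⱼx + εⱼ, Var(εⱼ) = 1 − λⱼ². Item score = number of thresholds exceeded (0–3). Factor score = posterior mean of η given the nine items. Rescaled score = PHQ-9 sample quantile at (rank − 0.5)/n. Twenty replicates of n = 1083. Counts below are the percentage × 1083.

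**Step 1: no overlap (β = 0), PHQ-9 against factor score.**

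| Loadings | Cross 10 | Differ by ≥ 3 points |
|---|---|---|
| Equal | 1.0% (11) | 0% |
| Mild | 2.5% (27) | 0.1% |
| Wide | 4.6% (50) | 4.7% |

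The 1.0% under equal loadings comes from splitting tied sums. Two further simulations agree. One, with loadings of 0.66–0.85, 0.55–0.85 or 0.72–0.90, gave about 22–44 patients crossing 10 (2.0–4.1%), against about 11 with equal loadings. Another, with complications also uncorrelated with depression, gave about 9, 24 and 41 for equal, mild and wide loadings.

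**Step 2: overlap present.** Neither factor score here used the complication–depression correlation, so the last step isolates the direct item paths.

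| Path | Loadings | PHQ-9 vs hdPHQ-9 | Factor score without item paths vs hdPHQ-9 | Ratio |
|---|---|---|---|---|
| 0.20 | Equal | 2.7% (29) | 2.4% (26) | 1.1 |
| 0.20 | Mild | 3.4% (37) | 1.6% (17) | 2.1 |
| 0.20 | Wide | 4.9% (53) | 0.9% (10) | 5.4 |
| 0.35 | Equal | 4.4% (48) | 3.9% (42) | 1.1 |
| 0.35 | Mild | 4.6% (50) | 2.8% (30) | 1.6 |
| 0.35 | Wide | 6.2% (67) | 1.7% (18) | 3.6 |

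With equal loadings nearly all reclassification is overlap removal. With wide loadings most of it is not.

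**Step 3: responsiveness with no overlap.** The standardized response mean for item weights w is d·Σwλ / √[(Σwλ)²·0.6² + Σw²(1 − λ²)]. It assumes mean latent change d, latent change SD 0.6 and item-residual correlation 0.5 over time. For wide loadings and d = 0.5:

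- Equal weights: Σλ = 5.88 and Σ(1 − λ²) = 4.98, so 2.94/√(12.45 + 4.98) = 0.704.
- Weights λ/(1 − λ²): both sums are 9.44, so 4.72/√(32.05 + 9.44) = 0.732.

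The ratio is 1.04 for wide, 1.01 for mild and 1.00 for equal loadings. In a separate simulation the factor score's response mean was 3–8% larger if affective items respond more than somatic ones, and 0–1% smaller if all items respond equally.

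**Step 4: which comparator isolates overlap.** Suppose the adjusted model also regresses the depression factor on complications. With no item paths at all, a score that omits every complication path still differs from the adjusted score: 1.0% (11 patients) cross 10 at correlation 0.3, and about 19–20 patients do at correlation 0.5 in another simulation. A third simulation gave about 8–17 patients, falling to 0 when only the direct item paths were dropped and the regression was kept.

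**The case against.** The strongest reply is that the overlap question is answered elsewhere. The SAP names standardized path coefficients as the result of the overlap analysis and adds bootstrap 95% intervals. That evidence does not depend on how the score is weighted, and it stands. A reader might infer that the plan cannot answer the overlap question at all; the documents do not support that. What the coefficients do not do is divide a difference in total score, classification or responsiveness into its two sources.

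Second, the plan draws few of the inferences at risk. It describes no reclassification analysis at 10, and its sentence on individual differences assigns no cause. The Protocol (Study design overview and timetable) also holds the hdPHQ-9 back from screening and from judging response until it has been assessed. This stands too. Crossing 10 matters only because the SAP keeps the PHQ-9 thresholds for later clinical use, with a web app. On responsiveness, the text available gives the one-sentence intention in the abstract and a timetable entry, so nothing can be said about how that analysis would attribute a difference.

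Third, the size rests on assumed loadings. A reader might infer that sizeable differences would appear without any overlap, or that re-weighting could explain everything. Step 1 shows no differences of 3 or more points with equal loadings and 0.1% with mild ones. Those stronger readings hold, at most, under widely unequal loadings.

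**Conclusion.** The point holds in a limited form. Two changes separate the PHQ-9 from the hdPHQ-9, and no planned score separates them. Differences between the two cannot be credited to overlap removal without a further comparator; with one, they can.

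The size is uncertain because it turns on loadings that the documents do not give. It is near nil if loadings are nearly equal. If they are unequal, roughly 2–5% of patients cross 10 with no overlap to remove. The responsiveness effect is roughly 0–8%. All of this assumes one factor and model-based scores computed from known parameters.

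The hdPHQ-9 itself, the item-level overlap estimates and the trial's remission outcome are unaffected. This is a cheap improvement, worth specifying in advance because nobody can know beforehand whether the loadings will be close to equal.

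**What to change.** In the SAP's hdPHQ-9 scoring text, add a second score. Fit the final model with only the direct complication-to-item (DIF) paths set to zero. Keep the same factor structure, the same covariates and any regression or correlation between the depression factor and complications. Extract factor scores with the same estimator and apply the same transformation.

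Report the PHQ-9, this no-DIF factor score and the hdPHQ-9 side by side for individual differences, any classification at the retained threshold, and responsiveness. Credit only the step from the no-DIF score to the hdPHQ-9 to overlap removal. Keep PHQ-9 against hdPHQ-9 as the practical comparison of two instruments.

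Do not use a model with every complication path removed as the comparator; Step 4 shows that it can register apparent overlap removal where there is none.

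Cost: one more model run and one more table column. No new data are needed, since the PHQ-9 and KDQOL are already collected at baseline and week 12, and the hdPHQ-9 does not change.

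### Unless path selection is repeated in each resample, the hdPHQ-9 bootstrap cannot show the overfitting bias the SAP says it will show

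*SAP*

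**What the plan says.** All of this is in the SAP under Statistical analyses and concerns Phase 1 (Aim A).

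- **Factor number.** An exploratory factor analysis of the nine items is run "to determine how many latent factors represent aspects of depression", guided by eigenvalues, parallel analysis and fit criteria.
- **Paths.** The work starts with "specifying the conceptual model". The initial model holds every potential DIF path. Then: "We will then make model comparisons and modifications to our initial model using multiple indices and statistics", including modification indices, together with clinical input. The target is "the most parsimonious model with all clinically relevant DIF paths of at least a small standardized path coefficient". No number is given for *small*, and no candidate list is written.
- **Validation.** After development "based on the entire sample, we will fit the model on a series of bootstrap datasets", averages and 95% intervals are taken "for each of the model parameters and fit indices across the bootstrap samples". The SAP also looks at how each person's scores "vary across the models derived from each bootstrapped sample".
- **Claimed purpose.** The bootstrap is to show "if there is any bias and sampling variation in the model parameters and associated hdPHQ-9 scores due to overfitting in the final model".

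The Protocol's timetable has a step for refining the conceptual model in the first two quarters. Its study design overview keeps the hdPHQ-9 out of screening and response decisions until the instrument has been assessed.

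**The concern.** Overfitting from a model search arises in the search. Paths that happen to look large in this sample are kept, and their estimates are then too large on average. A refit that skips the search takes the chosen structure as given and resamples around the selected estimates. Agreement between bootstrap mean and estimate is then automatic and says nothing about inflation.

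This is the only overfitting check the SAP states. A reader could take that agreement as evidence that the kept paths are sound, although the SAP names the path coefficients as the result of the analysis and intends the score for clinical use through a web app. The Protocol's planned comparison of PHQ-9 and hdPHQ-9 responsiveness also evaluates the instrument, but it does not test for overfitting.

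**Working it through.** **1. Is the structure fixed?** The SAP speaks of fitting *the* model and takes one average per parameter, which needs the same parameters in every resample. The plural in "vary across the models derived from each bootstrapped sample" could mean re-selection, but nothing says so. Selection cannot be repeated by program until clinical input and *small* become rules.

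**2. Inputs.** From the documents: about 1083 patients, nine PHQ-9 items, and 10 dialysis symptoms added to the KDQOL-36 (Protocol, Quality of life). Assumed: 20 candidate paths surviving a clinical screen, and cut-offs of 0.05 to 0.10. The SAP gives no bias figure or number of resamples, so there is no stated figure to reproduce.

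**3. False paths kept when every true DIF path is zero.** Expected number = 20 × 2 × (1 − Φ(cut-off/SE)).

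| Cut-off | SE 0.026 | SE 0.032 | SE 0.034 | Simulated range |
|---|---|---|---|---|
| 0.05 | 1.1 | 2.4 | 2.8 | 0.9–2.4 |
| 0.08 | 0.04 | 0.25 | 0.37 | 0.03–0.26 |
| 0.10 | 0.002 | 0.04 | 0.07 | 0–0.04 |

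For example, 0.05/0.026 = 1.92, the upper tail is 0.027, and 40 × 0.027 = 1.1. Simulated median SEs ran from 0.026 to 0.034. The formula at 0.034 slightly exceeds the simulated range. Adding p<0.05 to the 0.05 cut-off leaves 0.9–1.9 false paths, and p<0.01 leaves 0.2–0.7.

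**4. Inflation of a kept path.** For an estimate b distributed N(β, SE²), the quantity needed is E[b given |b| ≥ c]. With c = 0.10 and SE = 1/√1083 = 0.030:

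- true 0.08 averages 0.118 when kept (+0.038)
- true 0.10 averages 0.124 (+0.024)
- true 0.15 averages 0.153 (+0.003)
- true 0.20 averages 0.200 (no bias)

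**5. What the fixed refit reports.** The simulation used one factor, four-category items treated as continuous, complications correlated 0.4 and explaining 30% of the factor variance. Selection was by backward removal. There were 100 data sets with 200 resamples each. Entries are average kept coefficients.

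| Case | Sample | Fixed-refit bootstrap mean | Same structure, new patients |
|---|---|---|---|
| No true paths, cut-off 0.05 | 0.062 | 0.062 | 0.001 |
| Five true paths near 0.05, cut-off 0.05 | 0.069 | 0.069 | 0.029 |
| Five true paths near 0.10, cut-off 0.10 | 0.117 | 0.118 | 0.083 |

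The overstatement is 0.062, 0.039 and 0.035 (the rounded columns differ from this by up to 0.001). The fixed refit shows 0.000–0.001. Repeating selection shows 0.036, 0.028 and 0.026.

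A separate, simpler simulation treated the factor as observed and used 10 or 20 complications. Its fixed-refit bias was zero to within 0.0001 in all four settings. Actual selection bias was 0.009–0.011 on the all-path coefficients. After refitting the reduced model it was 0.016–0.060, which also includes bias from dropped paths. Re-selected path sets overlapped the original by only 66–71%.

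**6. Individual scores.** The average SD across resamples is 0.30 points (fixed) against 0.34–0.35 (re-selected) on the 0–27 scale.

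**7. Side note on fit indices.** Averaging fit over ordinary resamples adds roughly the degrees of freedom to chi-square. For a correct 107-df model under normal-theory ML this gives about 112 + 107 = 219; the simulation gave 221 against 112 in the data. RMSEA = √((221 − 107)/(107 × 1082)) = 0.031, against 0.006 in the data, and CFI moves from 0.998 to 0.976. Worse average fit is therefore not evidence of overfitting.

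**The case against.** **The wording is not settled.** The plural reference to models may mean re-selection. That is why the point is conditional. The reading does not rescue the plan, because the selection has no written rule to repeat. The SAP attaches a citation to the phrase about a small coefficient, and that source may define it. We cannot see it, and the same citation number is attached to the software.

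**The planned 95% intervals would warn the reader.** With SE 0.026 the half-width is 1.96 × 0.026 = 0.051. Then 0.069 ± 0.051 contains 0.029, and 0.117 ± 0.051 contains 0.083. This is a fair point, but these are averages, and the intervals are centred on the selected estimates with no correction for selection. With no true paths, 0.062 ± 0.051 has a lower limit of 0.011 and misses 0.001. At SE 0.034 it reaches below zero.

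**The scenarios are favourable to the concern.** Both cases with true paths place them near the cut-off, where selection bias is large. Step 4 shows that it fades by 0.15 to 0.20, and false paths are almost absent at a cut-off of 0.10. The simulated rule used neither fit nor modification indices, and the choice of factor number was not simulated. All of this limits the size of the effect but not its existence.

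**The instrument barely changes.** The fixed refit misses about 0.05 points of score SD. This stands and is the main reason to rate the issue low.

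**Re-selection is an imperfect cure.** This also stands; see the fix. The fit-index shift was not checked for categorical estimators, and the SAP names no estimator.

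**Conclusion.** The concern holds. As written, the SAP credits its bootstrap with showing overfitting bias, which a refit of a fixed structure cannot do for the selection step. That is a matter of logic and does not depend on the simulation settings. What the procedure validly gives is sampling variation conditional on the chosen model.

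The size is minor to moderate. Under the assumed 20 candidates and cut-offs of 0.05 to 0.10, kept paths near the cut-off are overstated by about 0.035 to 0.062 and the bootstrap shows at most 0.001 of it. Clear paths and individual scores are little affected. Early refinement of the conceptual model and the restriction to clinically relevant paths narrow the search, though no list results. Only the Phase 1 instrument is involved; remission at 12 weeks is not. Confidence in the sizes is medium, because the cut-off, candidate list and estimator are unstated.

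**What to change.** Choose one of two.

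**(a) Repeat the selection.** Before analysis, write down the clinically relevant candidate paths, the numerical value of *small* and the rule for the number of factors. Run this scripted selection in every resample. Report:

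- how often each path is included, for comparing paths and not as probabilities
- score variation across the re-selected models
- the shift in selected coefficients: the mean over kept paths of the resample coefficient minus the coefficient of the same structure in the original sample, signed by the resample estimate

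This costs scripting, computing time and one clinical session, and intervals widen. The shift recovered only part of the bias in the main simulation (0.036 of 0.062, 0.028 of 0.039, 0.026 of 0.035), though nearly all of it in the simpler one (0.010–0.012 against 0.009–0.011), so present it as a rough and probably low figure. Ordinary resamples also keep more false paths than the sample does (4.0 against 1.3 at cut-off 0.05 with no true paths). Inclusion frequency separates weakly: at that cut-off, kept false paths recur in about 61% of resamples and kept true ones in about 74%.

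**(b) Keep the fixed refit and change the claim.** Describe it as sampling variation conditional on the chosen model, and delete the reference to overfitting. This is one sentence.

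In both cases, report fit indices from the original sample and do not average them over raw resamples.
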